### **Secondary outcomes**

**Functional performance.** Functional performance will be assessed at  $T_0$ ,  $T_1$ ,  $T_2$ , and  $T_3$ . The test battery will consider aerobic capacity, upper and lower body strength, grip strength, shoulder mobility, and overall mobility. Aerobic endurance will be assessed using the 6-minute walk test, a standardized field test performed indoors in a 30-meter corridor with two turning points marked every 3 meters along the course, that has been considered valid and reliable for evaluating aerobic capacity in cancer patients . In this test, participants will be asked to walk the maximum distance possible in 6 minutes on a flat and hard surface, whereas the distance walked is the outcome . The arm curl and sit-to-stand tests will be used to test the lower and upper body strength, respectively, since they are valid and reliable in these populations . Handgrip strength will be measured using the JAMAR dynamometer since it has shown reasonable validity and reliability in measuring this variable among adults  $\geq 50$  years old and used in oncologic samples . While performing the handgrip test for each hand, participants will be instructed to stand upright with feet at hip width and elbows completely stretched while applying the maximum grip continuously for more than 3 seconds, and 30 seconds

of rest will be given between measurements . Handgrip strength will be considered to the nearest 0.1 kilograms, with each participant performing 2 attempts in each hand, and a best value will be considered . The timed up-and-go test will assess participants' overall mobility. Participants will be instructed to rise from a chair, walk 2.44 meters, turn around, walk back to the chair, and sit down . Shoulder flexion and abduction angular measures will be performed on both sides using a validated and reliable goniometer to measure this variable . Upper limb flexibility will be assessed using the back scratch test .

**Body composition.** Body composition will be measured through bioelectrical impedance (Impedimed Australia) at T0, T1, T2, and T3 at the beginning of each assessment . Data regarding weight, fat mass, lean mass, water percentage, bone mass, visceral fat, and phase angle will be collected from the scale . Participants will be asked to maintain their dietary patterns before the test and refrain from intense exercise the day before . The measurement will be performed under standardized conditions (i.e., in the morning, 8-hour fasting, bladder voiding before the assessment, controlled room temperature, and no exercise before the measurement) . The height measurement will be considered to the nearest 0.1 cm of the participants and will be performed using a balance-mounted stadiometer (SECA, Germany), with the participants standing and bare-footed . Body weight will be measured to the nearest 0.1kg with a digital scale (SECA, Germany) . BMI (kg/m^2) will be calculated from weight (kg) and height (m). Participants will be asked to maintain their dietary patterns before the test and refrain from intense exercise the day before . The measurement will be performed under standardized conditions (i.e., in the morning, 8-hour fasting, bladder voiding before the assessment, controlled room temperature, and no exercise before the measurement) .

**Physical Activity and Sedentary Behavior.** PA levels and SB will be assessed at T0, T1, T2, and T3 using a motion sensor (GT9 link, Actigraph) and the International Physical Activity Questionnaire Short-Form (IPAQ-SF) . Accelerometers have been previously reported as valid and reliable tools to objectively measure PA levels in general and clinical populations . Participants will be instructed to wear the device on an elastic belt on the non-dominant hip for 7 days during all waking hours, removing only to sleep . The sampling units (epochs) will be settled to 1s to ease data analysis and ensure the appropriate sensitivity of the device during low-intensity activities. The accelerometer counts will be categorized into sedentary, light, moderate, and vigorous activity levels according to specific established thresholds . Any interval of 60 or

more minutes with continuous zero counts, will be considered as non-wear time . The IPAQ-SF comprises 9 items that measure the weekly time spent on all intensities PA (i.e., light, moderate, and vigorous) and time spent sitting on week and weekend days. Total PA scores are calculated from the collected data and discriminated by intensity .

**Quality of life.** Quality of life will be assessed at T0, T1, T2, and T3, using the European Organization for Research and Treatment of Cancer Quality of Life Questionnaire (EORTC QLQ-C30). The specific module EORTC QLQ-BR45 will measure breast cancer-related quality of life. Both tools demonstrated adequate validity and reliability, specifically for cancer patients . The EORTC QLQ-C30 questionnaire consists of 30 items, grouped into 8 multi-item scales (i.e., functional: physical, role, emotional, cognitive, and social; symptom: fatigue, pain, and nausea), one global health status and quality of life subscale, and 6 single-item questions (dyspnea, insomnia, appetite loss, constipation, diarrhea, and financial difficulties) . The breast cancer module QLQ-BR45 comprises 5 functional sub-scales (body image, future perspective, sexual functioning, sexual enjoyment, breast satisfaction) and 7 symptoms sub-scales (arm symptoms, breast symptoms, endocrine therapy, skin mucositis, endocrine sexual symptoms, systemic therapy side effects, and upset hair loss), for a total of 45 items (the previous 23 items found in QLQ-BR23 plus 22 new items) . High scores on the functional scales determine better functioning, and high scores on the symptoms scale and body image mean higher issues . Because the QLQ-BR45 algorithm has not yet been validated, the QLQ-BR23 algorithm will be used to score the questionnaire .

### **Covariates**

**Demographics, physical activity and medical history.** Participants' demographic information (e.g., age, education, marital status, and economic status) and PA history will be collected through a general information questionnaire, and clinical history data will be retrieved from their medical records after they sign the informed consent form.

### **Plans to promote retention**

The conducting exercise professional will control participants' adherence to the exercise program through a presence registry collected by the research team member with access to the list of participants' numbers. After the session, the non-interventionist research team member will pass the presence list to the respective numbers of the participants for program adherence analysis. If a participant fails to attend a session, contact will be made to ensure the participant's welfare and motivate them to participate

in the next session. The data analysis will not consider participants who fail to attend 50% or more sessions. Positive feedback will be given to the participants during the sessions, as positive feedback is proven to enhance feelings of competence, enjoyment, and interest in the activity . Additionally, participants will be encouraged to keep an activity diary where they may register all activities performed autonomously. Participants will be contacted one week before the assessment to confirm their availability and presence. Data from participants who fail to perform the assessments during the intervention period will be excluded from data analysis. After the intervention, participants will be contacted monthly to check their well-being and keep their interest and motivation in engaging in the follow-up assessment.

\*\*\* Table 2\*\*\*

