### **Eligibility criteria**

Women aged  $\geq 18$  years with a BC stage I-III diagnosis, scheduled to receive neoadjuvant or adjuvant chemotherapy, and who have access to a computer will be considered eligible to participate in the study. Women already at the mid-stage of the chemotherapy treatments, with medical counterindication to perform the exercise intervention or physical assessments due to concomitant comorbidity, non-controlled health conditions or diseases, or psychological illness, currently enrolled in a structured exercise program, or women unable to complete the entire program (e.g., due to scheduled surgery or personal commitments) will be considered ineligible. Participants who get pregnant or have a worsening in their clinical condition during the intervention will be discounted from the program.

The exercise professionals who will perform the interventions and assessments must have an academic degree in Exercise Sciences and a specialization in exercise with cancer populations or receive education sessions with an exercise professional specialized in exercise for BC populations to acquire knowledge and skills to conduct exercise sessions online. Also, professionals who conduct the interventions will have to perform at least three simulated sessions among each other, supervised by a qualified peer, to guarantee consistency in the intervention application.

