### **Blinding (masking)**

Participants will be told they are part of an exercise intervention without any mention of a control group. The healthcare professionals responsible for the chemotherapy prescription and administration and registering all clinical information will be blinded to the participants' groups. None of the research team members will know the number of participants, so data analysis will be performed in a blinded setting. The exercise professional conducting the assessments will be blinded to the participant's number but not to which group the participant belongs. If, at any given moment, a participant reveals her number to a research team member, all posterior data from that participant will be disregarded. If a participant decides to leave the study or must abandon it due to health complications, the team member with the number information will be informed, and all further data will be disregarded from the analysis.

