### **Statistical methods**

All data will be analyzed using IBM SPSS (version 29.0). Factorial ANCOVAs with repeated measures will be used for the primary and secondary outcomes, adjusted for potential covariates (e.g., concomitant treatments, BC diagnosis, neo-adjuvant/adjuvant chemotherapy). Independent sample T-tests will be used to compare results between groups at each time point, considering chemotherapy completers versus non-completers . A Fisher's exact test will compare the proportion of participants who needed chemotherapy adjustments from those who did not . The intention-to-treat analysis will be conducted to ensure that all participants are included in the overall assessment, considering their compliance with the study protocol. The Last Observation

Carried Forward method will be used to input missing data values. A per-protocol analysis will also be conducted without participants who failed to complete at least 50% of the training sessions. Normality plots and Kolmogorov-Smirnov tests will be performed to test the normality of outcome variables. If normality is not satisfied, non-parametric tests will be applied (e.g., Krustal-Wallis). Mediators of change (i.e., mechanisms by which RDI) will be explored using structural equation modeling (AMOS 18.0) and multiple mediation analysis (PROCESS macro for SPSS). Putative candidates will include treatment (e.g., dose planned vs. given dose, planned cycles minimum/maximum, treatment interruption ratios, response to treatment, percentage of participants who needed dose adjustments, and the mean value of dose adjustment), and physiological (e.g., body composition, functional performance, handgrip strength, PA levels) variables. Mediation occurs when a causal effect of an independent variable occurs on a dependent variable, partly or entirely explained by a mediator. Indirect effects testing will be performed using Preacher and Hayes' procedures.

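### The retention section drops low attenders and women who miss assessments from the analysis, against the all-participants ITT, and RDI still in the medical record is discarded once a woman leaves

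*Protocol*

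**What the plan says.** Plans to promote retention gives two exclusions. On attendance: "The data analysis will not consider participants who fail to attend 50% or more sessions". On assessments: "Data from participants who fail to perform the assessments during the intervention period will be excluded from data analysis". Neither names an analysis set.

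Statistical methods describes an intention-to-treat (ITT) analysis meant to ensure that "all participants are included in the overall assessment, considering their compliance with the study protocol". For gaps, the Last Observation "Carried Forward method will be used to input missing data values" (LOCF). It then adds: "A per-protocol analysis will also be conducted without participants who failed to complete at least 50% of the training sessions". That per-protocol definition has no criterion for missed assessments.

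Blinding (masking) sets a further rule. It covers a woman who chooses to leave the study, and one who "must abandon it due to health complications, the team member with the number information will be informed, and all further data will be disregarded". If a woman reveals her number to the team, "all posterior data from that participant will be disregarded". Neither rule exempts RDI.

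Primary outcome takes planned and received chemotherapy from medical records and assesses RDI at T0, T1 and T2. Eligibility criteria foresees health-related departure: "Participants who get pregnant or have a worsening in their clinical condition during the intervention will be discounted from the program". The section on discontinuing or modifying allocated interventions also asks women whose condition worsens to stop the intervention. Neither section says whether their RDI stays in the analysis.

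**The concern.** There are two problems.

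First, the rules conflict. An analysis cannot include all participants and also drop those who attended little or missed assessments. The ITT sentence does not settle which rule governs, because its closing clause on compliance can be read as a qualification.

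Second, primary-outcome data that can be retrieved are thrown away. RDI does not depend on attending sessions or field tests, and the medical record goes on after a woman stops exercising. Discarding her later RDI and carrying an earlier one forward replaces a known final value with one that may precede her dose reductions or delays.

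The stake is the test of Hypothesis 1. Low attendance, missed assessments and leaving for health reasons are plausibly linked to poor tolerance of chemotherapy. Session burden differs by arm: two 60-minute sessions a week against one of 30 minutes (Interventions). Loss could therefore be both informative and unequal between arms.

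**Working it through.** **One woman, three answers.** Take a woman who stops for health complications after T1 and misses T2.

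- Plans to promote retention: she is excluded, if T2 counts as within the intervention period and one missed assessment is enough.
- Blinding (masking) with Statistical methods: she stays in, with her T1 RDI carried forward.
- Primary outcome: her true final RDI is in the medical record.

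If any missed assessment leads to exclusion, no missed assessment in that period is left for LOCF to fill. The 50% boundary is also unclear. The retention sentence can be read as excluding a woman who misses exactly half the sessions, while the per-protocol sentence keeps a woman who completes exactly half.

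**Single case under LOCF.** Suppose full dose on time to mid-course, then half dose. RDI is 1.00 at T1 and (1.0 + 0.5)/2 = 0.75 at the end. LOCF records 1.00, a success against the protocol's 85% cut-off, although the true value is below it.

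**Illustration of size.** The one input from the protocol is 98 women (82 × 1.20 = 98.4, Sample size), allocated 1:1, so 49 per arm. The rest is assumed:

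- No true effect.
- 25% of women tolerate chemotherapy poorly, with final RDI mean 0.75 (SD 0.10). The others average 0.96 (SD 0.04), and 5% of them are lost in each arm.
- T0 RDI is about 1.00 (SD 0.01).
- T1 RDI in poor-tolerance women averages 0.85, 0.90 or 0.95. T1 equals T2 plus the shift needed for that mean, plus noise of SD 0.02; the others have no shift.
- Interim RDI means dose to date against plan to date. The per-cycle wording in Primary outcome supports this but does not fix it.

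Let s be the share of poor-tolerance women lost in an arm. Bias is exercise minus control.

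- *Exclusion.* Arm mean = [0.25(1 − s) × 0.75 + 0.75 × 0.95 × 0.96] / [0.25(1 − s) + 0.75 × 0.95]. At s = 0.40: 0.7965/0.8625 = 0.9235. At s = 0.20: 0.8340/0.9125 = 0.9140. Bias = 0.0095.
- *T1 carried forward.* Bias = 0.25 × (difference in s) × (T1 mean − 0.75). For 40% against 20% and T1 mean 0.85: 0.25 × 0.20 × 0.10 = 0.005.
- *T0 carried forward.* Same form with 1.00: 0.25 × 0.20 × 0.25 = 0.0125.

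Type I error comes from simulation (20,000 replicates per scenario, two-sided 0.05) of a group-by-time F test over T0, T1 and T2 with Greenhouse-Geisser correction and no covariates. Ranges span the assumed T1 means (0.85 and 0.95 for exclusion; all three for LOCF).

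| Poor-tolerance women lost, exercise/control | Exclusion: bias; error | T1 carried: bias; error | T0 carried: bias; error |
|---|---|---|---|
| 20%/20% | 0; 4.8–4.9% | 0; 4.7–4.9% | 0; 4.8–5.0% |
| 30%/20% | 0.0046; 5.3–5.5% | 0.0025 to 0.0050; 5.2–5.5% | 0.00625; 5.8–6.0% |
| 40%/20% | 0.0095; 7.0–7.2% | 0.005 to 0.010; 5.3–8.2% | 0.0125; 9.2–9.8% |
| 60%/40% | 0.0107; 7.2–8.3% | 0.005 to 0.010; 5.4–8.3% | 0.0125; 10.0–10.5% |
| 20%/40% | −0.0095; 6.8–7.2% | −0.005 to −0.010; 5.5–7.6% | −0.0125; 9.2–9.7% |
| 60%/20% | 0.0202; 14.2–16.4% | 0.010 to 0.020; 7.0–20.1% | 0.025; 24.9–27.8% |

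A test of the time-averaged group effect rejects less often. At 60%/20% it gives 10–13%, 6–10% and 19–23% for the three rules.

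**The case against.** The attendance sentence may be shorthand. It sits in a retention section, uses the same 50% threshold as the per-protocol analysis, and Statistical methods names ITT separately. That reading is reasonable for attendance. It does not rescue the missed-assessment exclusion, which the per-protocol definition lacks and which conflicts with an all-participants analysis.

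Discarding data after exit and filling the gap by LOCF are consistent with each other. This is so: the second problem is a poor choice for a record-based outcome, not a contradiction.

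The texts on worsening health speak of leaving the program or the intervention, while the discard rule speaks of leaving the study. This also stands. Only the words on health complications in Blinding (masking) bear directly on RDI. The other two sections show that such departures are expected and leave the status of the data open.

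Continued access to records after exit is inferred, and the consent form is not shown. Withdrawal of consent is a separate matter and is not criticised here. The fix allows for it.

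The numbers are modest. Under the assumptions above the SD of final RDI is √(0.25 × 0.10² + 0.75 × 0.04² + 0.25 × 0.75 × 0.21²) = 0.109, so 0.0025 to 0.0125 is about 0.02 to 0.11 SD. The case therefore rests on the text and not on the simulated percentages.

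**Conclusion.** The concern holds and should be fixed before the analysis. As written, the protocol does not fix the population for the primary RDI comparison, and it discards final RDI values that the medical record may still hold. If the conflict is left, the choice among the rules could be made after results are seen.

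The size cannot be computed from the protocol, which gives no attendance or leaving rates by arm. In the illustration, a 10- to 20-point difference in loss gives a bias of 0.0025 to 0.0125 in mean RDI and a type I error of about 5% to 10.5%. The sign follows whichever arm loses more poor-tolerance women. Equal loss gives no bias, and only larger differences do substantial damage. These figures depend on the assumed tolerance mix, loss shares and to-date RDI, and they are not the error rate of the planned ANCOVA.

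**What to change.** - **Plans to promote retention:** confine the 50% attendance rule to the per-protocol analysis, with one wording of the boundary, and remove the missed-assessment exclusion from the primary analysis.
- **Statistical methods:** state that the primary RDI analysis includes every randomised woman in her allocated arm whatever her compliance. Delete or clarify the closing clause on compliance.
- **Blinding (masking):** exempt record-based RDI from both discard rules. Take RDI from the medical record to the end of chemotherapy unless the woman withdraws consent to record access.
- **Eligibility criteria, and the section on discontinuing or modifying interventions:** say that stopping the sessions does not by itself end this use of the record.
- **Missing RDI:** do not use LOCF where the record is available. Report women without record access separately or in a sensitivity analysis.

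The cost is a protocol amendment approved by the ethics committees involved (Protocol amendments) and a check that the consent wording covers record access after a woman leaves. No new data collection procedure is needed, since RDI already comes from medical records.

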### **Data management**

All the data collected in this study will be kept confidential, computerized, and encrypted in a database without any elements that may allow identification of the participants. After the participants have expressed interest and written informed consent, a number corresponding to the participant ID during the study will be provided. When the participant receives her ID number, all data inserted in the databases will not be directly linked to the participant's personal identification. A dataset will be created for each assessment time point. All datasets will be maintained by the members responsible for the investigation on a secure server of CIDEFES-UL for ten years and will be used exclusively for research purposes. Datasets used for specific analyses or to develop sub-studies will contain only the necessary variables and the demographical indicators provided to the research team members upon request to the leading investigator.

### **Statistical methods**

All data will be analyzed using IBM SPSS (version 29.0). Factorial ANCOVAs with repeated measures will be used for the primary and secondary outcomes, adjusted for potential covariates (e.g., concomitant treatments, BC diagnosis, neo-adjuvant/adjuvant chemotherapy). Independent sample T-tests will be used to compare results between groups at each time point, considering chemotherapy completers versus non-completers . A Fisher's exact test will compare the proportion of participants who needed chemotherapy adjustments from those who did not . The intention-to-treat analysis will be conducted to ensure that all participants are included in the overall assessment, considering their compliance with the study protocol. The Last Observation

Carried Forward method will be used to input missing data values. A per-protocol analysis will also be conducted without participants who failed to complete at least 50% of the training sessions. Normality plots and Kolmogorov-Smirnov tests will be performed to test the normality of outcome variables. If normality is not satisfied, non-parametric tests will be applied (e.g., Krustal-Wallis). Mediators of change (i.e., mechanisms by which RDI) will be explored using structural equation modeling (AMOS 18.0) and multiple mediation analysis (PROCESS macro for SPSS). Putative candidates will include treatment (e.g., dose planned vs. given dose, planned cycles minimum/maximum, treatment interruption ratios, response to treatment, percentage of participants who needed dose adjustments, and the mean value of dose adjustment), and physiological (e.g., body composition, functional performance, handgrip strength, PA levels) variables. Mediation occurs when a causal effect of an independent variable occurs on a dependent variable, partly or entirely explained by a mediator. Indirect effects testing will be performed using Preacher and Hayes' procedures.

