## **Objectives**

This study will investigate the effects of a structured, supervised, home-based combined exercise intervention with self-selected intensity on the chemotherapy completion rates of women with BC. We also intend to analyze the impact of this intervention on functional performance, body composition, PA levels, and quality of life. A 3-month follow-up will be performed to investigate short-term outcomes and active lifestyle sustainability post-intervention.

Hypothesis 1: Women in the intervention will have a better completion rate than those in the control group.

Hypothesis 2: Women in the intervention will present better functional performance, body composition, PA levels, and quality of life than the control group.

Hypothesis 3: In the post-intervention period, women in the intervention group will maintain a more physically active lifestyle than women in the control group.

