### **Sample size**

Considering this study design, sample size calculations were made for the primary outcome with a factorial variance analysis with repeated measures as reference statistical analysis, giving an initial estimation of 82 participants. Based on previous findings and considering a 20% dropout, the sample size was estimated at 98 participants with a moderate effect size ( $\alpha=0.05$ ; statistical power=0.80) according to Cohen's D calculations, using G\* Power 3.1 .

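### Secondary outcomes: the baseline value of the outcome is not named as a covariate, and no arm contrast at T3 is tied to Hypothesis 3

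*Protocol*

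**What the plan says.** The Protocol, Statistical methods, assigns one family of models to all outcomes: "Factorial ANCOVAs with repeated measures will be used for the primary and secondary outcomes, adjusted for potential covariates". The examples in brackets are concomitant treatments, diagnosis, and the neoadjuvant or adjuvant setting, introduced as examples only. The Outcomes and Covariates sections add demographics, physical activity history and clinical history. None of these places names the T0 value of the outcome being analysed.

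The secondary outcomes are measured at four visits. For example, "Functional performance will be assessed at" T0, T1, T2 and T3, and body composition, physical activity and quality of life follow the same schedule. Under Sequence generation, participants are randomised only once the baseline assessments are complete, so T0 is a true pre-randomisation baseline.

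Hypothesis 3 (Objectives) states that, after the intervention, "women in the intervention group will maintain a more physically active lifestyle than women in the control group". The Abstract and the Objectives both link this question to the 3-month follow-up, which is T3. No contrast at T3 is assigned to it.

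The only visit-specific test is this: "Independent sample T-tests will be used to compare results between groups at each time point". The sentence then goes on to mention chemotherapy completers and non-completers.

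**The concern.** There are two separate issues.

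**Baseline handling.** A repeated-measures factorial model for an outcome recorded at T0 to T3, without the T0 value among its covariates, most naturally treats T0 as one of four levels. The arms can differ at T0 only by chance. The arm contrast at a later visit is then either a comparison of changes from T0 or an unadjusted comparison at that visit. Both are less precise than adjusting for T0, a value the trial collects anyway. This affects every secondary outcome.

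**Hypothesis 3.** An overall arm or arm-by-time test combines all visits. It can be significant because of T1 and T2 when nothing remains at T3. Unless a T3 contrast is named, such a result could be reported as sustained activity.

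**Working it through.** **Inputs.** From the Protocol: four visits, T0 before randomisation, 1:1 allocation, alpha 0.05, "statistical power=0.80", and 82 before dropout. Assumed, because the Protocol gives no figures: a true difference of 0.5 SD (Cohen's f = 0.25), equal variances and equal correlations (compound symmetry), and rho = 0.5 with a range of 0.3 to 0.7.

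**Step 1: the plan's own figure.** The sample size was obtained "with a factorial variance analysis with repeated measures as reference statistical analysis", "giving an initial estimation of 82 participants". For the between-groups test, lambda = N f² m / (1 + (m − 1) rho) on 1 and N − 2 df.
- With m = 4, f = 0.25 and rho = 0.5: lambda = 82 × 0.0625 × 4 / 2.5 = 8.2, power 81%. With N = 80 power is 79.8%, so 82 is the smallest even N that reaches 80%.
- With m = 3 the answer is 86.

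The figure of 82 therefore fits a four-level repeated factor. This is only indirect support. The Sample size section ties 82 to the primary outcome, which is measured at T0, T1 and T2 only, and f and rho are assumed.

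**Step 2: precision at one visit (T2 or T3).** With 41 per arm and a difference of 0.5, lambda = (41/2) × 0.25 / v = 5.125 / v, where v is the variance for the method:
- adjusted for T0: v = 1 − rho² (79 error df)
- change from T0: v = 2(1 − rho) (80 error df)
- unadjusted t-test: v = 1 (80 error df)

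| rho | T0-adjusted: v, lambda, power | Change: v, lambda, power | t-test power |
|---|---|---|---|
| 0.3 | 0.91, 5.63, 65% | 1.40, 3.66, 47% | 61% |
| 0.5 | 0.75, 6.83, 73% | 1.00, 5.13, 61% | 61% |
| 0.7 | 0.51, 10.05, 88% | 0.60, 8.54, 82% | 61% |

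The ratio of T0-adjusted to change-score variance is (1 + rho)/2, that is 0.65, 0.75 and 0.85. With 98 analysed (49 per arm) the T0-adjusted power is 73%, 81% and 93%, against 54%, 69% and 89% for change and 69% for the t-test. The ordering is the same.

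**Step 3: Hypothesis 3 when nothing is sustained.** Let the arm differences at T0 to T3 be 0, 0.5, 0.5 and 0. Their mean is 0.25 and the sum of squared deviations is 4 × 0.0625 = 0.25.
- Arm-by-time test: lambda = (41/2) × 0.25 / (1 − rho) = 7.32, 10.25 and 17.08 on 3 and 240 df. It is significant 60%, 76% and 95% of the time.
- Arm main effect over T0 to T3: difference 0.25, variance (1 + 3 rho)/4. It is significant 37%, 29% and 25% of the time.
- T0-adjusted average of T1 to T3: difference 1/3, variance (1 + 2 rho)/3 − rho². It is significant 61%, 64% and 76% of the time.
- Contrast at T3 alone: 5%.

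The arm-by-time test is not in error here, because an interaction does exist. It answers a different question from Hypothesis 3. The third line shows that moving T0 to a covariate does not cure this; only the T3 contrast does.

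**The case against.** **The protocol never says that T0 is a level.** This is right. It is an inference from the model type and the visit schedule, and an open list of examples does not rule out the T0 value as a covariate. Such detail may also sit in a statistical analysis plan that is not shown. What remains is that the Protocol does name a model and covariates for these outcomes, and its text points to the less precise version. If T0 adjustment is intended, the same short edit is needed.

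**The t-tests already give a T3 comparison.** If they compare arms, they give an unbiased comparison at T3, because T0 precedes randomisation. But the closing phrase about completers leaves open which groups are meant, and no baseline adjustment is stated. They neither settle Hypothesis 3 nor show that a T3 arm comparison is absent.

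**Larger gains could be quoted.** With an effect at T1 to T3 and rho 0.5, a reader might set 93% power for a T0-adjusted T1-to-T3 average against 56% for the overall arm effect or 63% for arm-by-time. This overstates the gain for the contrasts that matter, since Hypotheses 2 and 3 call for T2 and T3. It also mixes a 3-df with a 1-df test: with T0 still a level, a 1-df contrast of T0 against the T1-to-T3 mean already has 78%.

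**Other stronger readings.** A reader might infer that keeping T0 as a level is what lets T1 and T2 drive Hypothesis 3; Step 3 shows otherwise. A reader might also treat T2 as a visit during the programme. The Protocol labels it post-intervention. Accelerometers are handed out a week before the field tests, so overlap with the last sessions is possible, but it is not stated.

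**Conclusion.** The point holds as two limited defects in the plan for the secondary outcomes. The primary outcome is not part of it.

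First, the T0 value of the outcome is not named as a covariate. On the natural reading this loses efficiency: at rho 0.5, single-visit power is 61% where 73% is available. The T0-adjusted analysis has the highest power at each of the three correlations tried. A repeated-measures arm-by-time analysis remains valid, and a reader should not infer bias, because T0 is measured before allocation.

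Second, Hypothesis 3 has no contrast of its own, so a significant overall test could be taken as sustained activity when the arms do not differ at T3. This stands however baseline is handled.

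The percentages are illustrations. Apart from the 82 they rest on an assumed 0.5 SD effect, compound symmetry and rho between 0.3 and 0.7. The change should be made, but the trial's main conclusion does not depend on it.

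**What to change.** In Statistical methods, give the secondary outcomes their own sentence:
- the repeated response is the values at T1, T2 and T3
- the T0 value of the same outcome is a covariate, alongside arm, visit, arm-by-visit and the other prespecified covariates
- the T0-adjusted arm contrast at T2 answers Hypothesis 2, and the one at T3 answers Hypothesis 3.

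State which groups the t-tests at each time point compare. If they are meant to compare arms, replace them with these contrasts for the secondary outcomes.

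The cost is analysis wording only. T0 is already collected, no visit or procedure changes, and the model can be fitted in the SPSS version already named.
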